8.4.1. Procedure of documentation and report of adverse events

All adverse events arised during the study will be documented and reported to the local ethics committee. All adverse events will be additionally analyzed

8.5. SUBSEQUENT MONITORING AFTER SERIOUS ADVERSE EVENTS

In the case of serious adverse events causing drop-out of a participant. This participant will be directed to psychiatric/psychotherapeutic services will be contacted by the study team as soon as possible to assure that they are in professional care. Subsequent monitoring of participants completed the study or dropped out is not provided.

9. STATISTICAL ANALYSIS

9.1. SAMPLE SIZE CALCULATION

We aim to detect a small to medium between-group effect size (Cohen's d) of 0.35 at post-treatment. The chosen effect size is reasonable since CAU being an active alternative treatment may decrease between-group outcome differences and a smaller effect size was considered to be irrelevant from a clinical point of view. Based on a-level of .05 and a power of .95 using a single-level repeated measures ANOVA power analysis with G*Power, the sample size needed is approximately 55 participants per group and 110 for the total sample. Our secondary aim is to find outcome predictors within participants who complete iCBT-I. In order to enlarge this sample, participants from the CAU group will get access to the iCBT-I program after the follow-up period.

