3. STUDY DESIGN

- a) The proposed study is a multicenter parallel-group add-on superiority RCT comparing an active treatment condition (iCBT-I plus CAU) to CAU alone.

After signing the IC form, participants will receive an e-mail with the link to the Qualtrics Survey Software (Qualtrics, Provo, UT, USA), where they complete baseline assessment and receive the individual allocation code. On completion of baseline measures, subjects will be automatically assigned by the randomization function of Qualtrics Survey Software to either iCBT-I plus CAU or CAU group using single block randomization. Neither participants nor referring specialist nor the research team have foreknowledge and/or control over randomization and the allocation procedure. Following randomization, the participants will receive an automated email regarding their group allocation and a description of future steps. In case they were allocated to the treatment group, their individual code will provide an access to the iCBT-I program.

Participants in the control group will get access to the iCBT-I program after the 5-month follow-up (3 months after post-assessment) provided they completed the follow-up assessment and still fulfill eligibility criteria. In this group, an additional assessment will be conducted eight weeks after providing access to the CBT-I program to enlarge the sample for the analysis of outcome predictors.

The research team, except the trial coordinator, will be blind to allocation. Coding allocation form, along with the participant's real name and address noted in the IC form, will be stored in the password-protected computer of the trial coordinator. Participants will not be blind to treatment allocation and will receive information about their randomization outcome via email. Questionnaires and sleep diaries will be completed entirely online under the participant's individual code.

3.1.OUTCOMES

3.1.1. The primary endpoint of the present study is the change of Insomnia Severity Index (ISI) from pre- to post-treatment and at follow-up.

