4.2.1. RESTRICTED CONCURRENT THERAPY

not applicable

5. SAMPLE SIZE.

110 patients with CI will be recruited through referrals from health care practitioners, i.e., neurologists specialized in somnology.

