7.3. EXCLUSION CRITERIA

1. Refusal of the further participation;
2. Pregnancy
3. Exacerbation of Anxiety or depressive disorder as measured with the Beck Depression Inventory (BDI-II; score > 28) and the Beck Anxiety Inventory (BAI; score > 25)—assessed by the questionnaires at any timepoint
4. Increase of suicidality risk — as measured with BDI-II suicidality subscale score >1 at any timepoint

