9.2. STATISTICAL ANALYSIS OF EFFECTIVENESS

The main analyses will be conducted on the intention-to-treat sample. Clinical effects of treatment will be evaluated using mixed-model repeated-measures analyses where the pre-post comparisons of all outcome measures will include time as a within-group variable and the condition as a between-group variable. An incremental cost-effectiveness ratio (ICER) will be calculated to obtain the additional costs of iCBT-I in comparison with control condition. Cohen's d will be reported for all within-between comparisons based on estimated means and the pooled standard deviation from the observed means at pre- and posttreatment. To test significance of the difference between the number of responders in each treatment condition, we will use χ^2 -test. Regression analyses will be used to identify predictors of treatment outcome. We will test models using Akaike/Bayesian Information Criteria to select an optimal model with predictors of treatment outcome.

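### Section 9.1 claims 95% power for d = 0.35 with 55 per group, but the planned time-by-condition test has about 44% at an assumed T0–T1 correlation of 0.5 and reaches 95% only near 0.87

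*Combined protocol and SAP*

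**What the plan says.** Section 9.1 sets the target: "We aim to detect a small to medium between-group effect size (Cohen's d) of 0.35 at post-treatment". It adds that "a smaller effect size was considered to be irrelevant from a clinical point of view", so 0.35 is the plan's own threshold of relevance. The calculation is described as alpha .05 and "a power of .95 using a single-level repeated measures ANOVA power analysis with G*Power", with the result that "the sample size needed is approximately 55 participants per group and 110 for the total sample". The section does not give the effect size f that was entered, the number of measurements, the correlation between them, or which G*Power repeated-measures test was chosen.

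The analysis is in section 9.2: a mixed-model repeated-measures analysis on the intention-to-treat sample in which "the pre-post comparisons of all outcome measures will include time as a within-group variable and the condition as a between-group variable". Cohen's d is to be standardised by the pooled SD of the observed scores, not by the SD of change. The primary endpoint in section 3.1.1 is the "change of Insomnia Severity Index (ISI) from pre- to post-treatment and at follow-up".

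On numbers, section 5 states that "110 patients with CI will be recruited through referrals from health care practitioners". The number needed and the number to be recruited are therefore the same.

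**The concern.** A between-group d and the f of a repeated-measures interaction are on different scales. Converting with f = d/2 is right for two groups compared on a single measurement. It is not right for a 2×2 interaction when the groups start level and differ only at the second time point. A total of 110 looks too small for 95% power at d = 0.35 unless T0 and T1 scores are very highly correlated, and the plan states no correlation.

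What is at stake is how a null result would be read. With .95 power at the smallest relevant effect, a non-significant result would carry only a 5% risk of having missed that effect. If true power is nearer one half, a non-significant result says little about whether a relevant effect exists, yet readers of section 9.1 would take it as strong evidence against one. The comparison concerned is the primary one.

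**Working it through.** **Inputs from the plan.** d = 0.35 at post-treatment, alpha .05, power .95 and 55 per group (9.1); pre-post model with time and condition (9.2); randomised parallel groups, so equal baseline means are expected (section 3).

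**Assumptions.** T0–T1 correlation ρ (not given; 0.3 to 0.8 shown), equal SDs at T0 and T1, a two-sided test, and 110 complete patients unless noted.

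**Formula.** For the within-between interaction with k = 2 groups and m measurements, the noncentrality is λ = f²·N·m/(1−ρ), with df1 = m−1 and df2 = (N−2)(m−1).

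**Step 1: reproduce the plan's figure.** Take f = d/2 = 0.175, m = 2, ρ = 0.5.
- N = 110: λ = 0.030625 × 110 × 2/0.5 = 13.475, power .953.
- N = 108: power .9499, just short of .95.

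So 110 is exactly the sample size these inputs give.

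**Step 2: the f that d = 0.35 implies.** With cell differences of 0 at T0 and d at T1, removing the main effects leaves residuals of ±d/4 in each of the four cells. Hence f = d/4 = 0.0875. Conversely, f = 0.175 corresponds to a difference of 4 × 0.175 = 0.70 SD.

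**Step 3: power of the planned test at d = 0.35.** At ρ = 0.5, λ = 0.00765625 × 110 × 2/0.5 = 3.369 and power is .444. This is the same as a two-sample t test on change, whose SE is √(4(1−ρ)/55): 0.35²/(4 × 0.5/55) = 3.369.

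| | ρ = 0.3 | 0.5 | 0.7 | 0.8 |
|---|---|---|---|---|
| Power, 55 per group | .34 | .44 | .65 | .82 |
| Risk of missing d = 0.35 | 66% | 56% | 35% | 18% |
| d detectable at 80% power | 0.64 | 0.54 | 0.42 | 0.34 |
| d detectable at 95% power | 0.82 | 0.69 | 0.54 | 0.44 |
| Total N for .95 at d = 0.35 | 596 | 428 | 258 | 172 |
| 95% CI half-width (SD) | 0.45 | 0.38 | 0.29 | 0.24 |

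Power reaches .95 with N = 110 at ρ = 0.873. Simulated t tests on change scores (40,000 runs each) gave .336, .441, .651 and .821 for the first row.

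The half-width is t(.975, 108) × √(4(1−ρ)/55). At ρ = 0.5 it is 0.378 SD, so even an observed difference of zero would not exclude 0.35.

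**Step 4: other readings of the analysis.**

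| Reading | Power at ρ = 0.5 | ρ needed for .95 |
|---|---|---|
| Unadjusted comparison at T1 | .44 (any ρ) | none |
| d standardised by the SD of change | .44 (any ρ) | none |
| Three time points, 2-df interaction, effect sustained at T2 | .45 | 0.86 |
| Baseline-adjusted comparison at T1 | .56 | 0.86 |
| Mean of T1 and T2, effect sustained | .56 | 0.83 |
| One-sided test on change | .57 | 0.85 |

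**Step 5: dropout.** Section 9.1 makes no allowance, although section 7.3 provides for exclusion during the study, for example on depression or anxiety scores "assessed by the questionnaires at any timepoint". With an assumed 20% loss, counting only complete pairs (44 per group), power is .28, .37, .55 and .73 at ρ = 0.3, 0.5, 0.7 and 0.8.

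**The case against.** The strongest reply is that section 9.1 shows too little to convict it of a specific error. The f = d/2 explanation is worked back from the answer, the text says only approximately 55, and other inputs also reach .95 at N = 110 if the correlation is left free (f = 0.175 with three measurements and ρ = 0.36; f = 0.0875 with three measurements and ρ = 0.84). This stands as far as the cause goes, which remains an inference. It does not rescue the claim: whatever was entered, .95 power for d = 0.35 needs a correlation that the plan neither states nor supports.

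The 44% figure also rests on an assumed correlation. That is so, and the whole range should carry weight. At 0.8, though, power is still .82.

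The complete-pairs dropout row is slightly pessimistic, because a likelihood-based mixed model keeps the baseline data of patients who miss T1. With 55 at T0 and 44 at T1 per group, missing at random, power is about .30, .39, .57 and .74, which is at most about .02 higher. The 20% itself has no source in the documents, and section 7.3 gives no rate.

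Finally, 110 patients may suit larger effects, and section 1.2 describes short-term effects as medium to large. But section 9.1 itself chose 0.35, on the ground that active usual care may shrink the difference.

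**Conclusion.** The concern holds. As written, section 9.1 does not support .95 power at d = 0.35 for the test in section 9.2. With 55 per group and complete data, power is .34 to .82 over correlations of 0.3 to 0.8, and .44 at 0.5. Every alternative reading that can reach .95 at all needs a correlation of about 0.83 or more. These figures rest on equal SDs at T0 and T1, equal baselines by randomisation, a two-sided .05 level except where marked one-sided and, for three time points, a common correlation.

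That 110 came from entering f = d/2 is the likely explanation, but it is not proven and the conclusion does not depend on it. The text must be corrected, because the overstatement sits at the effect the plan itself names as the smallest that matters.

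**What to change.** Keep N = 110. In section 9.1, state the test, f, the number of measurements and the assumed T0–T1 correlation with its justification, and replace the 0.35/.95 claim with figures for the section 9.2 analysis. Possible wording:

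> For the time-by-condition test at T1 with 55 per group, two-sided .05, equal SDs at T0 and T1 and an assumed correlation of 0.5, power is about 44% for d = 0.35, 80% for d = 0.54 and 95% for d = 0.69. For d = 0.35 it is 34%, 65% and 82% at correlations of 0.3, 0.7 and 0.8. Dropout lowers these figures. A non-significant result will be interpreted from its confidence interval against 0.35.

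This changes only the text of 9.1 and needs no extra patients, but the stated power becomes less favourable.

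An option that gains some power is to amend 9.2 as well, to a baseline-adjusted comparison at T1. At a correlation of 0.5 this gives about 56% for d = 0.35, 80% for d = 0.47 and 95% for d = 0.60. Section 9.1 should quote those figures only if 9.2 is amended to match.

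### The power of 0.95 in section 9.1 allows for essentially no missing post-treatment ISI; that shortfall is modest, and a larger, separate one comes from how d = 0.35 was turned into 110

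*Combined protocol and SAP*

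**What the plan says.** Section 9.1 targets a "between-group effect size (Cohen's d) of 0.35 at post-treatment". It sets the error rates with "Based on a-level of .05 and a power of .95", names the tool as a "single-level repeated measures ANOVA power analysis with G*Power", and concludes that "the sample size needed is approximately 55 participants per group and 110 for the total sample". It does not say which effect was tested, how many measurements were entered, or what pre-post correlation was assumed.

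Section 5 sets recruitment at the same number: "110 patients with CI will be recruited through referrals from health care practitioners". Neither section mentions attrition, inflation or replacement.

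Section 7.3 lists grounds for leaving after entry, starting with "Refusal of the further participation". The others are pregnancy, BDI-II or BAI above the severe cutoffs, and a raised suicidality score. Section 8.5 adds drop-out after a serious adverse event. Section 9.2 specifies an intention-to-treat mixed model for pre-post comparisons, without a missing-data assumption or method.

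**The concern.** The number needed and the number recruited are the same, so the stated power holds only if practically every randomised participant gives a T1 ISI. The plan itself names ways in which participants leave. The course is self-paced, the questionnaires are completed online and there is no payment, so complete data cannot be taken for granted. The mixed model does not repair this: a participant with only a baseline ISI adds almost nothing to the group contrast in pre-post change.

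The stated power matters for reading the result. Section 9.1 calls effects below 0.35 clinically irrelevant. A null result set against a claimed power of 0.95 would look like strong evidence against any relevant benefit. If the true power for d = 0.35 is well below 0.95, that reading is not justified.

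**Working it through.** **Inputs from section 9.1:** alpha 0.05, power 0.95, d = 0.35, N = 110 (55 per arm). **Inferred, because they return 110:** within-between interaction, two groups, m = 2 measurements, correlation rho = 0.5, and f = d/2 = 0.175. **Assumed:** the loss rates, since the documents give none.

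**1. Reproducing 110.** Power is the upper tail of a noncentral F with 1 and N − 2 degrees of freedom and noncentrality lambda = f² × N × m / (1 − rho).

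At N = 110: lambda = 0.030625 × 110 × 2 / 0.5 = 13.475, power 0.953. At 109 power is 0.952, and at 108 it is 0.9499. The smallest even N reaching 0.95 is 110, so the figure is the complete-data answer with no margin beyond rounding.

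Other settings with f = 0.175 do not return 110: three measurements at rho = 0.5 give 86; two measurements at rho = 0.3, 0.6 and 0.7 give 152, 88 and 66; the between-group main effect with two measurements at rho = 0.5 gives 322.

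**2. Effect of loss before T1, same formula.**

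| Assumed loss | Analysed N | lambda | Power |
|---|---|---|---|
| 0% | 110 | 13.475 | 0.953 |
| 10% | 99 | 12.13 | 0.932 |
| 20% | 88 | 10.78 | 0.901 |
| 30% | 77 | 9.43 | 0.858 |
| 40% | 66 | 8.09 | 0.800 |

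The correlation matters about as much as the loss. At rho = 0.6, power with 20% loss is 0.952. At rho = 0.4, power is 0.913 with no loss.

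**3. What f = 0.175 means in this test.** In a 2 × 2 interaction, a between-group difference in change of delta SD shifts each cell by delta/4, so f = delta/4. Then f = 0.175 means delta = 0.70, twice the stated d. As a check, at rho = 0.5 the change score has variance 2 × (1 − 0.5) = 1, and lambda = 0.70² × 110/4 = 13.475, the same as in step 1.

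**4. Power for a between-group d = 0.35 at T1.** For a two-sided two-sample t test with n per arm, the noncentrality is d × √(n/2). With baseline adjustment, d is replaced by d/√(1 − rho²); at rho = 0.5 this is 0.35/√0.75 = 0.404.

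At n = 55, unadjusted: 0.35 × √27.5 = 1.835, power 0.444. Adjusted: 0.404 × √27.5 = 2.119, power 0.556.

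| Assumed loss | n per arm | Unadjusted | Adjusted, rho = 0.5 |
|---|---|---|---|
| 0% | 55 | 0.44 | 0.56 |
| 10% | 49.5 | 0.41 | 0.51 |
| 20% | 44 | 0.37 | 0.47 |
| 30% | 38.5 | 0.33 | 0.42 |

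A change-score analysis at rho = 0.5 gives the same power as the unadjusted comparison. A higher correlation helps: by normal approximation, adjusted power with no loss is 0.63, 0.73 and 0.86 at rho = 0.6, 0.7 and 0.8. None reaches 0.95.

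**The case against.** A reader might infer that any loss breaches 0.95, that all four grounds in section 7.3 remove the T1 ISI, and that attrition is why 0.95 is not reached. The documents do not support these readings.

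- One loss leaves power at 0.952. Two losses take it to 0.9499, a trivial breach, and section 9.1 calls its numbers approximate.
- Two of the four grounds are questionnaire scores. Section 3.2 collects these at the same visits as the ISI and schedules no questionnaire visit between baseline and T1, although section 8.4 mentions assessment during the intervention. A participant flagged at T1 would normally have a T1 ISI. Refusal, pregnancy and drop-out after a serious adverse event are the routes that could lose it, and section 8.1 says the method is not associated with serious adverse events.
- The requirement in sections 3 and 3.2 that controls complete follow-up before receiving the course concerns week 20. It says nothing about T1 and may encourage controls to stay.
- Starting from 0.95, the inferred calculation is still at 0.86 with 30% loss and reaches 0.80 only near 40%.
- The figures of 0.44 and 0.56 arise with no loss. They belong to the effect-size entry and must not be counted as the cost of attrition.

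All of this stands, and it limits the size of the attrition point. It does not remove it: the recruited number has no margin, withdrawals are foreseen, and no completion rate is stated. The text between sections 5 and 7.1 was not available for this check, so a replacement rule there cannot be excluded. Section 9.1, where an allowance belongs, contains none.

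**Conclusion.** The point holds in a limited form. It is a missing planning assumption, not an arithmetic slip, because 110 reproduces exactly under one set of inputs. With those inputs, attrition costs about 2 percentage points of power at 10% loss, 5 at 20% and nearly 10 at 30%. These sizes rest on assumed loss rates and on the inferred test, measurements and correlation.

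The main reason 0.95 should not be claimed is separate. For the d of 0.35 at post-treatment that section 9.1 names, 110 complete participants give about 0.44, or 0.56 with baseline adjustment at correlation 0.5. Attrition then lowers these further, to 0.37 and 0.47 at 20% loss. Inflating recruitment for drop-out would not close that gap.

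**What to change.** Keep N = 110 and rewrite section 9.1 so that it states:

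- the test, the number of measurements and the pre-post correlation;
- an assumed share of participants with a T1 ISI, labelled as an assumption;
- one power figure for the between-group d = 0.35 at that analysed number, for the analysis that will be used.

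For example, with 20% missing and 88 analysed, the figure would be about 0.37 for an unadjusted comparison, or about 0.47 for a baseline-adjusted one at correlation 0.5. The claim of 0.95 should be removed.

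The cost is rewording one section and a less favourable stated power. No extra participants are needed, and the conduct of the trial does not change.

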Both pharmacotherapy, CBT-I (or BBT-I) and their combinations produce treatment response only in 60-67% of patients and remission only in 42-55%. A reasonable way to improve the clinical effectiveness is determining the target group of patients that benefits most of iCBT-I. Some studies have shown that efficacy of CBT-I is related to the severity of maladaptive cognitions and behavior. As there is not much knowledge about predictors of iCBT-I treatment efficacy, in this trial, we will deliberately analyze psychometric, anamnestic and sleep characteristics which may act as predictors of CBT-I, which may also be relevant in iCBT-I. Specifying predictors of effectiveness of iCBT-I will give the opportunity to develop more individualized therapeutic decision-making procedure and will be important for economic reasons. In the longer term, obtaining of portrait for patient who benefit from iCBT-I will give us cues to understanding insomnia in whole and its subtypes.

It would be the first implementation of on-line behavioral treatment for insomnia in Russia and the first attempt to develop online materials for chronic insomnia treatment which would simplify the insomnia treatment improve patient adherence. In view of a huge demand of specialists in CBT-I development and approbation of this program will fill this gap in clinical practice. All the participants will have access to care as usual (CAU), which let us reconstruct real clinical situation along the whole course of the study. To our knowledge, this is one of the first studies considering iCBT-I in clinical settings.

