1.2. PREVIOUS CLINICAL APPLICATION

Structure of the investigated treatment course Internet-based CBT-I (Sleepsy[©]) is based on the already established program iSLEEP – internet-based self-help against insomnia that was already tested in previous study in Bern Universitz, Switherland. Short-term effectiveness of iCBT-I was high with effect size from median to large. The longest follow-up period in the studies of iCBT-I was 3 years. After this period there was no difference in the primarz outcomes between intervention and control group, but participants of intervention group used sleep aids significantky less than control. Moreover, there were no adverse events throughout the follow-up

Since the overwhelming majority of iCBT-I randomized controlled trials (RCTs) were conducted in research settings with recruitment via internet and advertisement, it is unclear if the promising results from efficacy studies can be transferred to routine clinical practice. For this study participants will be recruited from the doctor's office to ensure proper diagnostics and exclusion of other diseases affecting depth and length of sleep. It may be that patients, referred to iCBT-I directly from doctor's office, have active and more severe sleep complaints, and therefore are more motivated to benefit from the treatment

2. Aim of the study

Aims:

1. to investigate clinical effectiveness and cost-effectiveness of the internet-based CBT-I program Sleepsy in comparison with care as usual (CAU) among patients with CI recruited from clinical settings.

2. to investigate predictors of treatment outcome by analysis of baseline characteristics.

Tasks:

[figure not shown]
- Baseline assessment of recruited participants;
- Randomization;
- Treatment of intervention group by means of iCBT-I course;
- Post-treatment assessment of all participants;
- Follow-up assessment of all participants;
- Comparison of primary and secondary outcomes in intervention and control groups;
- Treatment of control group by means of iCBT-I course;
- Post-treatment assessment of control group participants;
- Statistical analysis of response predictors.

Hypothesis

- iCBT-I is more effective and cost-effective than CAU in clinical settings
- The analysis will help us identify the typical sleep pattern and obtain psychological portrait of those who benefits from behavioral treatment

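### The Background and second hypothesis ask who benefits from iCBT-I, but predictors are sought among treated completers with no stated arm-by-predictor term, which answers a prognostic question only

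*Combined protocol and SAP*

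**What the plan says.** Two kinds of language appear.

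**Benefit language.** Section 1 (Background) gives as a way to improve effectiveness "determining the target group of patients that benefits most of iCBT-I", and says that knowing the predictors "will give the opportunity to develop more individualized therapeutic decision-making procedure". The second hypothesis in section 2 expects to find a typical sleep pattern and to "obtain psychological portrait of those who benefits from behavioral treatment".

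**Outcome language.** Aim 2 in section 2 is "to investigate predictors of treatment outcome by analysis of baseline characteristics", and the task list has "Statistical analysis of response predictors". Section 9.1 gives the population: "Our secondary aim is to find outcome predictors within participants who complete iCBT-I". Section 9.2 gives the method: "Regression analyses will be used to identify predictors of treatment outcome", with the model chosen by AIC/BIC. It names no candidate variables, no population for these regressions and no interaction.

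Section 3 offers the program to controls after the week-20 follow-up, "provided they completed the follow-up assessment and still fulfill eligibility criteria", and assesses them again eight weeks later to enlarge the predictor sample. Section 3.1.2, item 2, defines response as a fall in ISI of more than 7 points from baseline. Section 3.2 identifies baseline as T0.

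**The concern.** Who benefits from iCBT-I is a question about how the difference between iCBT-I plus CAU and CAU alone varies with a patient characteristic. It needs both arms. Among treated patients only, improvement mixes the program's effect with natural course, regression to the mean and concurrent CAU, which section 9.1 itself calls an active alternative. A characteristic that predicts improvement equally well under CAU would still enter the profile.

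Three details add to this:

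- Completion happens after randomisation and is not defined (modules or assessments), so completers are a selected group.
- Controls treated later are selected again, by finishing T2 and remaining eligible, and have no concurrent control.
- If their response is counted from T0, change that occurred under CAU alone is credited to the program.

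At stake is the second aim and the individualised decisions that the Background hopes to draw from it.

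**Working it through.** **The plan's own figure.** The documents give no sample size for the predictor analysis. The only figure is 110 (55 per group) for the primary comparison. It reproduces as a repeated-measures within-between test with f = 0.35/2 = 0.175 and, as assumptions, two time points and correlation 0.5. Then lambda = 0.175² × 110 × 2/(1 − 0.5) = 13.5 on 1 and 108 df, and power is 0.953. I use 110 below only as the number randomised.

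**What each analysis can estimate.**

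| Question | Data needed | In the plan? |
|---|---|---|
| Who does well under iCBT-I (prognosis) | treated patients | yes: 9.1, 9.2 |
| Who gains more from iCBT-I than from CAU (benefit) | both arms, arm-by-predictor term | not stated |

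The data for the second row are already planned. Section 3.2 lists the same questionnaires for both arms at T0, and a common set including the ISI at T1.

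**Illustration under the plan's selection rule.** All inputs except 55 per arm, the 0.35 effect and the use of AIC/BIC are assumptions. In SD units, T1 ISI = 0.5 × T0 ISI − 0.35 × arm + √0.75 × (−r x + √(1 − r²) e). The predictor x acts identically in both arms, so there is no differential benefit.

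| Share of simulated trials | r = 0.2 | r = 0.3 | r = 0.4 |
|---|---|---|---|
| Treated only, n = 55: x kept by AIC | about 53% | 81% | 95% |
| Treated only, n = 55: x kept by BIC | 31% | 62% | 87% |
| Both arms, N = 110: arm-by-x kept by AIC | 16–17% | 16–17% | 16–17% |
| Both arms, N = 110: arm-by-x kept by BIC | 3–4% | 3–4% | 3–4% |

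The last two rows agree with large-sample theory. AIC keeps one extra term when its likelihood-ratio statistic exceeds 2, and P(χ²₁ > 2) = 15.7%. BIC needs ln 110 = 4.70, and P(χ²₁ > 4.70) = 3.0%. A single 5% test flags the null interaction in about 5% of trials.

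**Precision of the interaction.** For a balanced binary predictor with residual SD 1, SE = √(16/N).

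- N = 110: SE = 0.381 and the 95% half-width is 1.96 × 0.381 = 0.75 SD. Two-sided 5% power is 15/26/45% for arm effects differing by 0.35/0.5/0.7 SD.
- N = 88 (assumed 20% loss): SE = 0.426, half-width 0.84 SD, power 13/22/38%.
- N for 80% power at 0.5 SD: 16 × (1.96 + 0.84)²/0.25 = about 502.

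**Reference point for controls treated later.** Section 3.2 puts T0 at week 0, T2 at week 20 and T3 at week 28. A change from T0 to T3 spans 28 weeks, of which 20 (20/28 = 71%) precede access to the program.

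**The case against.** The operative parts of the plan agree with one another. Aim 2, the task list and sections 3, 9.1 and 9.2 all speak of outcome or response predictors, and a regression in treated patients is a legitimate answer to that. The mismatch is confined to the Background and one hypothesis bullet. This stands, and it means that rewording is a sufficient remedy if prognosis is all that is wanted.

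A reader might infer that the treated-only analysis produces false positives. It does not: the percentages in the first two rows of the simulation table are correct detections of a real prognostic association. They mislead only if read as benefit. Nor do the documents exclude an interaction, since section 9.2 is silent on it. But the only population named for predictors is iCBT-I completers, and no arm contrast can be estimated there.

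The interaction model has low power and most intervals will be inconclusive. This also stands. It is a reason for an exploratory label, and it does not turn a treated-only model into evidence of benefit.

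The reference-point issue is conditional. Section 9.2 does not say that the regression outcome is binary response, and requiring controls still to be eligible limits how much earlier improvement could be credited.

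**Conclusion.** The concern holds as a mismatch between part of the stated purpose and the analysis. The plan can describe who does well under iCBT-I plus CAU, in a sample selected after randomisation. It cannot say who gains more from iCBT-I than from CAU. The structural conclusion needs no assumed numbers. The retention rates rest on the assumed correlations and the single-predictor model; the power figures rest on a balanced binary predictor and one test.

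A reader might infer that the trial's main result is in doubt. It is not: the between-arm comparison of ISI does not depend on this analysis.

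A separate inconsistency came up. Section 3.1.2, item 7, intends the PID-5-FBF as a predictor, but it is in none of the T0–T3 lists in section 3.2. If those lists are followed, the personality predictors are not collected. This does not bear on the interaction question.

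**What to change.** In section 9.2:

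1. **Treated-only regressions.** Label them prognostic. Include everyone given access, not only completers. Adjust for pre-treatment ISI (T0 for the iCBT-I arm, T2 for controls treated later) and for treatment wave. For those controls, measure change and response from T2.
2. **Any claim about who benefits.** Add an exploratory model in all randomised participants of T1 ISI on T0 ISI, arm, predictor and arm-by-predictor, for a short list of T0 questionnaire and general variables fixed in advance. Report each interaction estimate with its 95% interval. Do not select the interaction by AIC.
3. **If item 2 is not adopted.** Reword the Background and the second hypothesis as predictors of outcome under iCBT-I.

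Separately, reconcile sections 3.1.2 and 3.2 on the PID-5-FBF.

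The cost is plan wording and a few models on data already scheduled. There are two downsides. Precision is poor (about ±0.75 SD at N = 110), so the benefit models can only be exploratory. And the sleep-pattern part of the hypothesis stays prognostic: under section 3.1.2, item 1, diary recording starts after randomisation and on different platforms in the two arms, so diary variables should stay out of the interaction model.
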